### 3.1.2. Statistical Hypothesis Test

The rate of endpoint events will be compared between the two groups using a negative binomial model. The model will be adjusted for the number of heart failure hospitalizations within 12 months prior to enrollment to adjust for any potential imbalance between the two arms.

The statistical hypothesis test for the primary endpoint, stated in terms of a null and alternative hypothesis is:

$$H_0: \beta_1 = 0$$

$$H_a: \beta_1 < 0$$

where  $\beta_1$  is the natural log of the ratio of events per patient-year between groups (treatment/control). The treatment effect of the device as a relative reduction in the endpoint event rate is estimated by  $1 - \exp(\beta_1)$ . The parameter  $\beta_1$  is referred to as  $\theta$  in the BADR where the likelihood function for the joint negative binomial model is described.

### 3.1.3. Group sequential design

Morbidity and mortality will be evaluated using a frequentist group sequential design. The group sequential boundaries are specified by the Hwang-Shih-DeCani spending function with  $\gamma = -3$ . The parameter  $\gamma$  indexes the Hwang-Shih-DeCani spending function such that  $\gamma = -4$  is similar to an O'Brien-Fleming boundary and  $\gamma = 1$  is similar to a Pocock boundary. Analyses are planned based on data accumulated through the time at which 140, 180, 240, and 320 primary endpoint events have occurred in the trial. These three interim analyses and a final analysis after 320 events have occurred are planned due to uncertainty regarding the treatment effect size. A large treatment effect would result in stopping the study at one of the interim analyses while a more moderate treatment effect would require more events in order to conclude that the treatment effect is statistically significant.

The boundaries of the Hwang-Shih-DeCani spending function at each interim analysis will be determined based on the estimated information fraction at the time of analysis and at any previous interim analyses. The information fraction for a negative binomial model estimate of the treatment effect comparing two randomized arms is defined in Mütze et al. (2018). The information fraction depends on the event rate in each arm, the length of follow-up of each patient, and the variance (dispersion) of the negative binomial distribution. A consistent estimate of the information can be obtained by plugging in maximum likelihood estimates from the interim data. At each interim analysis, the total information of the trial at 320 events will be estimated based on simulation through 320 events using the negative binomial model parameter estimates (e.g., dispersion) obtained at the time of interim analysis. The estimated information at the time of the interim analysis divided by the simulated total information at 320 events will provide the information fraction at the interim analysis to determine the spending function boundary.

#### 3.1.4. Analysis Method

The hypothesis test will be based on a Z-statistic for the estimate of  $\beta_1$  from a negative binomial regression model. Although randomization is expected to result in balanced baseline covariates between the two arms, the model will include the baseline covariate of number of heart failure hospitalizations 12 months prior to enrollment to adjust for any potential imbalances between the two arms. In SAS (version 9.4 code) this model is fit as follows:

```
proc genmod;  
  model nev=trt hfh / dist=negbin offset=lfutime;  
run;
```

where nev is the number of events, trt is an indicator variable of randomization to the treatment arm, hfh is the number of heart failure hospitalizations within the 12 months prior to enrollment, and lfutime is the logarithm of the follow-up time. The Z-statistic (Z) is the parameter estimate for trt divided by the associated standard error. A Wald test one-sided nominal p-value is calculated by calculating the standard normal tail probability  $\Phi(Z)$ . This simplified model has previously been demonstrated to provide treatment effect estimates in strict agreement with those obtained with the more complex joint model defined in the BADR.

Success for demonstrating a reduction in morbidity and mortality is determined by the z-statistic crossing the group sequential boundary at one of the pre-specified analyses whose timing is determined by reaching pre-specified numbers of events.

#### 3.1.5. Analysis Population

The analysis population for the prospective data to be analyzed for this endpoint is all randomized subjects with a baseline NT-proBNP < 1600 that have post-activation follow-up. Endpoint follow-up evaluation for the morbidity and

mortality endpoint begins at the actual device implant (device subjects) or anticipated implant date that is recorded prior to randomization (medical management subjects). All events adjudicated by the CEC as meeting the endpoint event definitions will be included in the analysis. Both prospective and previously analyzed follow-up time periods and events will be included in the analysis.

### 3.2. Focused Endpoints

Based on discussions in November 2022 between the FDA and the BeAT-HF Steering Committee, as well as CVRx and an independent statistician, a set of focused and clinically relevant endpoints were pre-specified. The purpose of these pre-specified focused endpoints is to provide a structure to evaluate the totality of the data while limiting the potential for a type I error inflation among non-primary endpoints. The primary endpoint and analysis method remains unchanged, and the analysis of all focused endpoints will be performed independently from the results of the primary endpoint.

The pre-specified focused endpoints were identified prior to the unblinding of the data. These focused endpoints are a subset of the endpoints and analyses pre-specified in the Statistical Analysis Plan, with minor clinically justified and statistical clarifications. The analyses of the focused endpoints will be based on descriptive statistics, nominal two-sided 95% confidence intervals and p-values. No statistical adjustment for multiple comparisons will be made.

These analyses are intended to support any updated labeling for patients with heart failure.

#### 3.2.1. Rate of CV Mortality and HF Morbidity (Expanded Definition)

The objective is to demonstrate that treatment with the BAROSTIM NEO System, relative to medical management, reduces the rate of cardiovascular mortality or worsening heart failure that leads to hospitalization (expanded definition) or emergency room visit (expanded definition), cardiac assist device or heart transplant.

As this endpoint may include additional events due to the expanded definition, and the planned censoring (see Section 2.1), statistical hypothesis (see Section 2.1.2), analysis method (see Section 2.1.4) and population (see Section 2.1.5) is the same as the primary endpoint, the endpoint should have at least the power of the primary endpoint.

The expanded definition is defined in the CEC Charter and includes hospitalizations that are determined to be heart failure hospitalizations by a CEC consensus yet may not have all of the documentation available.

Note: This analysis may be updated to include all events that are adjudicated up to the final Clinical Events Committee meeting, regardless of ENDPOINT CLOSING DATE defined in Section 2.

**Rationale:** This endpoint is consistent with the primary endpoint except that it includes events that are hospitalizations / ER visits that are determined to be heart failure hospitalizations by a CEC consensus yet may not have all the documentation available. This enables events that are of equal significant to the primary endpoint events to be included in evaluating the M&M benefit.

### 3.2.2. Win Ratio Expanded – MLWHF QoL

A Win Ratio analysis will be performed using the components of the morbidity and mortality endpoints as well as Minnesota Living with Heart Failure Quality of Life at 12 months. The following hierarchy will be used:

1. CV Death
2. Heart transplant or LVAD
3. Number of hospitalizations or emergency department visits for heart failure using the expanded definition of heart failure
4. Number of unscheduled clinic visits w/IV diuretic using the expanded definition for heart failure
5. Change from baseline in Minnesota Living with Heart Failure Quality of Life at 12 months (5 points is minimal clinically relevant difference).

The Win Ratio analysis will use all pairs of subjects between the two study arms to determine the number of wins and losses for the treatment versus control arm.

For each pair, follow-up is defined by the shorter of the follow-up periods. For example, if one patient has 1 year of follow-up and the 2nd has 2 years, the follow-up time used for comparison is 1 year. If the first subject in a pair is censored prior to an event time for the second subject in a pair, that pair is a tie. This produces the shared duration of follow-up for each pair, avoiding bias due to differential follow-up.

Any missing data for MLWHF QOL at 12M will be handled with single imputation via fully conditional specification linear regression based on baseline characteristics (MLWHF QOL, age, sex, LVEF, NYHA, NT-proBNP) and 6M MLWHF QOL. Single imputation is sufficient for the win ratio analysis, as the goal of the imputation is to produce an individual value for a missing pair to facilitate breaking ties.

The p-value comparing the two arms will be calculated using the Schoenfeld-Finkelstein method. A 95% confidence interval for the Win Ratio will be calculated using the bootstrap method.

**Rationale:** The Win Ratio incorporates both clinical events as well as patient-centric quality of life, providing a comprehensive evaluation of the impact of the therapy for patients. These events are weighted based on severity, where cardiovascular death is considered a more serious event than other non-fatal events such as LVAD / heart transplant, which is followed by heart failure hospitalizations. The last comparison is Minnesota Living with Heart Failure

Quality of Life ensuring that a clinically meaningful improvement in quality of life is evaluated.

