## 3. PRIMARY AND FOCUSED ENDPOINTS

### 3.1. Primary Endpoint: Rate of CV Mortality and HF Morbidity

#### 3.1.1. Rate of Cardiovascular Mortality and Heart Failure Morbidity

The objective is to demonstrate that treatment with the BAROSTIM NEO System, relative to medical management, reduces the rate of cardiovascular mortality or worsening heart failure that leads to hospitalization or emergency room visit, cardiac assist device or heart transplant.

Subjects will be censored at the time of a terminal event (i.e., death, permanent cardiac assist device, heart transplant, or novel implantation of a device to receive Cardiac Contractility Modulation) or end of follow-up, whichever occurs first.

The end of follow-up for analysis of morbidity and mortality will occur on the last date where adverse event status is known for the subject. This definition of follow-up time ensures that only time periods where morbidity and mortality status has

been assessed are included. End of follow-up is defined for each subject as the later date of:

- Last study visit
- Last date of adverse events reported in the database:
  - If last adverse event is a hospitalization, use discharge date
  - If last event is not a hospitalization, use resolution date if resolved, else use onset date
- Date subject completed the final, protocol defined end of study visit (note: this only occurs at end of study)

This end of follow-up date will be used to calculate follow-up time for the negative binomial model.

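### The focused win ratio imputes a 12-month MLWHF score for a subject known to have died of a non-cardiovascular cause, so that subject can beat a living one at tier 5; the effect is modest and the repair is small.

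*SAP*

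**What the plan says.** SAP 3.2.2 sets the hierarchy. Tier 1 is cardiovascular death. The other tiers are:

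- Tier 2: "Heart transplant or LVAD"
- Tier 3: "Number of hospitalizations or emergency department visits for heart failure using the expanded definition of heart failure"
- Tier 4: "Number of unscheduled clinic visits w/IV diuretic using the expanded definition for heart failure"
- Tier 5: "Change from baseline in Minnesota Living with Heart Failure Quality of Life at 12 months (5 points is minimal clinically relevant difference"

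Follow-up for a pair is the shorter of the two subjects' periods. If one subject is censored before the other's event, the pair is a tie. The SAP says of this: "This produces the shared duration of follow-up for each pair, avoiding bias due to differential follow-up".

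For tier 5 the rule is "Any missing data for MLWHF QOL at 12M will be handled with single imputation", using baseline characteristics and the 6-month MLWHF. The stated reason for a single draw is that "the goal of the imputation is to produce an individual value for a missing pair to facilitate breaking ties". The section names no exception for subjects who have died and no worst-rank rule. It does not require 12 months of shared follow-up before tier 5 is used.

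For the primary endpoint, SAP 3.1.1 says: "Subjects will be censored at the time of a terminal event (i.e., death, permanent cardiac assist device, heart transplant". SAP 5.4 censors non-cardiovascular deaths at the date of death. SAP 5.8 (Clinical Stability) counts any death before 12 months as worsened. Protocol 4.3.4 treats a death as cardiovascular unless a specific other cause is identified, so deaths of unknown cause fall in tier 1.

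**The concern.** Take a subject who dies in month 4 of an infection adjudicated as non-cardiovascular. No tier counts that death. It only shortens the shared follow-up, so the pair is often level on tiers 1 to 4 and goes to tier 5. The 12-month MLWHF is absent because the subject is dead. The rule for any missing value still supplies one, and the subject is then compared as if alive. An imputed score of this kind estimates nothing that could have been observed.

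The win ratio is one of a few focused endpoints meant to support labeling, reported with nominal intervals and p-values (SAP 3.2). Its rationale says that events are ordered by severity, and letting a death win on quality of life contradicts that. Only device subjects undergo the implant, so the two arms need not have equal numbers of non-cardiovascular deaths.

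**Working it through.** The plan states no power or expected value for the win ratio, so there is no figure to reproduce. The check sizes the rule.

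**Inputs from the documents**
- Analysis population 319 (SAP Section 1), taken as 159 v 160 (split assumed): 159 × 160 = 25,440 pairs.
- Control rate 0.4 per patient-year and dispersion 1.7 (SAP 8.1). The parametrisation is not explicit, so the negative binomial shape k is taken as 1.7 or as 1/1.7.
- MLWHF change SD from Protocol Table 3: 2.8 × √64 = 22.4 and 3.1 × √54 = 22.8. Use 22.5.
- Tier 5 margin: 5 points.

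**Assumed**
- Non-cardiovascular death before month 12 in 1% to 4% of each arm, at month 6 on average.
- No true effect on events or MLWHF.

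**1. Chance that a dead-versus-living pair reaches tier 5.** The probability of no event by time t is (k/(k + 0.4t))^k. At t = 0.5 this is 0.828 (k = 1.7) or 0.842 (k = 1/1.7). Both subjects are event-free with probability 0.828² = 0.69 or 0.842² = 0.71.

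**2. Chance that tier 5 decides the pair.** The difference of two changes has SD 22.5 × √2 = 31.8. P(dead subject better by at least 5) = Φ(−5/31.8) = 0.438. By symmetry the loss probability is 0.438, leaving 0.124 tied, so 0.876 are decided. If the imputed value is a bare prediction with little spread, the win probability is about 0.41.

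**3. Share of all pairs decided on a dead subject's imputed score** = 2q(1 − q) × 0.69 × 0.876.

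| q per arm | 2q(1 − q) | share decided |
|---|---|---|
| 1% | 1.98% | 1.2% |
| 2% | 3.92% | 2.4% |
| 4% | 7.68% | 4.6% |

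All-pairs simulations that also vary the time of death and admit pairs level on non-zero event counts give 1.2% to 1.3%, 2.4% to 2.5% and 4.6% to 5.1%.

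**4. Shift in the win ratio if the dead subject instead ranks last in tier 5.** Each dead-versus-living pair at tier 5 loses 0.438 of a win and gains 0.562 of a loss for the dead subject's arm, a total of 1.0.
- At 3% (device) v 1% (control), the two kinds of pair are 0.03 × 0.99 = 2.97% and 0.01 × 0.97 = 0.97% of all pairs. The net is 2.0%.
- If about 49% of pairs reach tier 5 over a 12-month horizon, ties are 0.49 × 0.124 = 6%, so wins and losses are each about 47%.
- The shift in the log win ratio is about 0.020 × 0.69 / 0.47 = 0.03. Simulation gives 0.03 to 0.035.
- At equal mortality the two kinds of pair cancel, and simulation gives 0.01 or less.
- With 1% v 3% the shift reverses sign.

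**5. Against sampling error.** The simulated SD of the log win ratio is about 0.13 (range 0.10 to 0.15). 0.03/0.13 = 0.23 and 0.04/0.13 = 0.31.

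**6. All-cause death in tier 1.** A small simulation (12 runs per scenario) compared the rule as written with all-cause death in tier 1. The win ratio moved from 1.016 to 0.959 at 3% v 1%, and from 1.060 to 1.107 at 1% v 3%. The log shifts are ln(1.016/0.959) = 0.06 and ln(1.107/1.060) = 0.04. The individual win ratios are noisy, but both methods were applied to the same simulated data.

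**The case against.** The strongest reply is that the effect is small and rests on a death rate that the documents do not give. That stands: even a 2-point imbalance moves the result by well under one standard error.

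A reader might infer that the rule hides device harm. The documents do not support this. The shift favours whichever arm has more non-cardiovascular deaths, and no imbalance is stated. Deaths of unknown cause count as cardiovascular, and several listed implant risks, such as stroke, embolization and carotid rupture, are vascular. All-cause mortality is reported separately (SAP 5.10), SAP 5.8 counts every death before 12 months as worsened, and complications, which include deaths (Protocol 3.5.6), are tabulated under SAP 6.4 and 6.5.

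A reader might also extend the point to cardiovascular deaths whose partner's follow-up ended first. That needs a partner censored before a death that itself fell within 12 months. With follow-up of 2.3 years or more it contributes almost nothing, and the tie sentence may close such pairs anyway.

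The hierarchy itself is defensible, because it uses the components of the primary endpoint, whose fatal component is cardiovascular death. The SAP also never says outright that a value absent because of death counts as missing, and a programmer might exclude it. The main SAP and the CEC Charter were not available and could contain a rule. But the text reviewed gives no such instruction, and a pre-specified analysis should not depend on that choice. If the tie sentence is read as final for the pair, pairs whose living partner has no later event still reach tier 5.

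**Conclusion.** The point holds for deaths before month 12 with a specific non-cardiovascular cause. As written, the rule gives such a subject a 12-month score and lets it defeat a living subject, in about 41% to 44% of the pairs that reach tier 5 if there is no true MLWHF effect. On assumed mortality of 1% to 4% per arm, about 1.2% to 5% of all pairs are decided this way. The log win ratio moves by about 0.01 or less with equal mortality and by about 0.03 to 0.04 at 3% v 1%. These sizes depend on the assumed death rates, the SAP event rate and an MLWHF SD taken from earlier 6-month data.

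This is a modest flaw in one focused endpoint. The primary negative binomial analysis is untouched. It is worth correcting because the rule gives a wrong result for the pairs it affects and is cheap to repair.

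**What to change.** Add to SAP 3.2.2, for tier 5:

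- Do not impute MLWHF for a subject known to have died before month 12. Rank that subject below a partner known to be alive at month 12, and score two such deaths as a tie.
- Keep the stated imputation for all other missing values, including subjects withdrawn or lost with no known death.
- State that this is an explicit exception to the shared-follow-up rule, justified because tier 5 is measured at a fixed 12 months.

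Also add a sensitivity analysis with all-cause death in tier 1. The tier 5 rule alone does not stop a subject with a non-cardiovascular death from winning at tiers 3 or 4. For example, a subject who dies at month 3 with no heart failure event would still beat a living partner with one hospitalization in those 3 months.

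The cost is a few sentences and a few lines of code, with no new data. The win ratio may become slightly less favourable if non-cardiovascular deaths occur in the device arm.

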## 7. COVID-19

On March 13, 2020, the US announced a national emergency declaration due to the COVID-19 pandemic. Due to the changes in care patterns and accessibility to healthcare, as well as the interruption of logistics at trial sites, COVID-19 has had a significant impact on the execution, results and interpretation of clinical trials. These issues have been discussed globally by medical groups as well as governmental agencies. In addition, there are examples from recent clinical trial that have demonstrated the potential impact of COVID-19 on the effectiveness of therapies.

To adjust for, measure and understand the impact of COVID-19, several changes, including the collection of key data, were prospectively made to the trial in early 2020, including:

- Completion of randomizations at a total of 467 subjects randomized (13 less than then 480 randomized originally planned).
- To minimize the exposure of subjects, site personnel and CVRx personnel to COVID-19, protocol required follow-up visits could be completed via telephone. This reduced or delayed the completion of testing required at certain follow-up visits (e.g., six minute hall walks, blood draws). These deviations were specifically collected and noted as related to COVID-19.
- All site monitoring is done remotely until the site, CVRx and the monitor agree that an in-person meeting is safe and necessary.
- Device programming, if possible and appropriate, may be done remotely.
- A COVID-19 case report form (see Section 8 for copy of form), dedicated to understanding the impact of COVID-19 on subjects in the trial, was designed and implemented based on a template developed by the Heart Failure Collaboratory ([www.hfcollaboratory.com](http://www.hfcollaboratory.com)). This form is required for all subjects for all follow-up visits starting on or after 01April2020, depending on IRB approval and/or site implementation. The form includes questions such as: “Since the last visit did the subject FEEL THE NEED to go to an emergency department or hospital for their heart failure BUT DECIDED NOT TO because of concerns about COVID-19”.
- The CEC Charter was updated to collect COVID-19 relatedness to endpoint. Specifically, for each adjudicated event the following evaluation of the impact of COVID was documented:
  - If COVID-19 is the primary reason for hospitalization, the committee indicates a secondary reason for hospitalization.

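### SAP 3.2.2 fills missing 12-month MLWHF with one unseeded draw from a model without randomized arm, which tends to weaken the QoL tier of the win ratio and makes its nominal p-value depend on the seed

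*SAP*

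**What the plan says.** The win ratio in SAP 3.2.2 is one of the focused endpoints. Its last tier compares change in MLWHF from baseline to 12 months, with the threshold given as "5 points is minimal clinically relevant difference".

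On missing values the section says: "Any missing data for MLWHF QOL at 12M will be handled with single imputation via fully conditional specification linear regression based on baseline characteristics". The full list of predictors is "based on baseline characteristics (MLWHF QOL, age, sex, LVEF, NYHA, NT-proBNP) and 6M MLWHF QOL". Randomized arm is not in it, and the text does not say that imputation is done within arm. The justification is: "Single imputation is sufficient for the win ratio analysis, as the goal of the imputation is to produce an individual value".

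On inference it says "The p-value comparing the two arms will be calculated using the Schoenfeld-Finkelstein method" and "A 95% confidence interval for the Win Ratio will be calculated using the bootstrap method". It gives no seed and no sensitivity analysis for missing QoL, and it does not say whether the bootstrap repeats the imputation.

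SAP 3.2 makes the focused endpoints nominal, two-sided and unadjusted for multiplicity, and intends them to support labeling.

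**The concern.** Two features of the stated method need attention.

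**Arm is missing from the imputation model.** The model used to fill in an outcome should contain the variable whose effect is being estimated. Without arm, imputed 12-month values reflect treatment only as far as the other predictors carry it. The one listed predictor that can carry it is 6-month MLWHF. Where that is missing as well, nothing in the model separates the arms.

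**Only one draw is made.** The SAP argues that a pair needs a value and one draw supplies it. But each tie so broken enters the win ratio, its p-value and its interval. If the draw is random and no seed is fixed, two correct runs on the same data can report different results.

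The SAP treats arm differently elsewhere. SAP 4.1 imputes events separately by arm in a sensitivity analysis, and the MLWHF regression in SAP 3.2.4 includes the randomization group. No reason is given for leaving it out here.

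**Working it through.** The documents give no effect size, power or missing-data rate for this win ratio, so there is no planned figure to reproduce. The size of the problem was assessed by simulation.

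**Inputs from the documents**
- 319 subjects (SAP 1), allocated 1:1 (protocol 3.1).
- Control event rate 0.4 per patient-year, censoring-event fraction 0.18, dispersion 1.7 (SAP 8.1). Dispersion was treated as a gamma shape, which fits SAP Table 4, where the smaller value 1.4 is labelled large overdispersion.
- Mean follow-up 2.3 years (protocol 4.3.3).
- Earlier studies, protocol Table 3: MLWHF difference −17.4 − 2.1 = −19.5; SE = √(2.8² + 3.1²) = 4.18 (stated 4.2). SD of change: 2.8 × √64 = 22.4 and 3.1 × √54 = 22.8.
- Protocol Table 4: −21.6 − 3.5 = −25.1; SE = √(3.6² + 3.7²) = 5.16 (stated 5.2). Both tables reproduce.
- Six-month QoL in those studies: 64 + 54 = 118 of 146 subjects, so 28/146 = 19% without a value. This is only an anchor for the range below.

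**Assumptions not in the documents**
- 12-month MLWHF missing in 10, 20 or 30%, plus early deaths and LVADs (about 16, 25 and 34% in total).
- Correlation between 6 and 12 months 0.6, varied from 0.4 to 0.8.
- QoL effect of 19.5 points with an event rate ratio of 0.8, or 8 points with 0.9.

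**Method.** All pairs were compared over shared follow-up: CV death, then transplant or LVAD, then HF event count, then MLWHF change with the 5-point threshold. The clinic-visit tier was not modelled. Each missing value was filled by one FCS draw, with and without arm. The z-statistic used a U-statistic variance in place of the test named in the SAP. There were 300-400 datasets per scenario, and 2,000 under the null.

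**Why the direction depends on the 6-month effect.** With equal SDs, the slope on 6-month MLWHF is roughly the correlation. When 6-month values are observed, the imputed difference between arms is then roughly 0.6 × the 6-month effect:
- sustained 19.5 points: 0.6 × 19.5 = 11.7, below 19.5, so shrinkage;
- 19.5 waning to 8: 11.7, above 8, so slight inflation;
- 8 growing to 19.5: 0.6 × 8 = 4.8, below 19.5, so shrinkage.

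When 6-month values are also missing, the imputed difference is near zero.

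**Shrinkage, sustained 19.5-point effect.** Entries are log win ratio without arm divided by log win ratio with complete data; win ratios in brackets.

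| 12M missing | 6M observed | Half also lack 6M | All also lack 6M |
|---|---|---|---|
| 10% | 0.97 (1.70→1.68) | 0.95 (1.68→1.64) | 0.93 (1.69→1.62) |
| 20% | 0.95 (1.70→1.65) | 0.90 (1.67→1.59) | 0.84 (1.70→1.56) |
| 30% | 0.92 (1.68→1.61) | 0.85 (1.72→1.58) | 0.78 (1.70→1.51) |

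For example, ln 1.51 / ln 1.70 = 0.412 / 0.531 = 0.78. With arm in the model, the win ratio was 1.67-1.71, against 1.67-1.72 with complete data.

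Other scenarios:
- Correlation 0.4 / 0.8 (20% missing, 6M observed): 0.92 / 0.97.
- 8-point effect, half also lacking 6M: 0.95 / 0.88 / 0.84 at 10 / 20 / 30% missing. Rejection fell from 0.390 to 0.350, 0.445 to 0.347 and 0.435 to 0.318 (Monte Carlo SE of each about √(0.43 × 0.57 / 400) = 0.025).
- 19.5 points waning to 8 (20% missing, 6M observed): 1.05. Growing from 8 to 19.5: 0.88.

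**Seed dependence.** Over 60 seeds on the same data, the SD of z was 0.12-0.26. At z = 1.96, one SD either way gives:
- SD 0.12: z from 1.84 to 2.08, two-sided p from 0.066 to 0.038;
- SD 0.26: z from 1.70 to 2.22, p from 0.089 to 0.026.

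The p-value fell on both sides of 0.05 in 5-20% of datasets with the large effect, 12-30% with the 8-point effect and 45% with the waning effect. These shares are rough. One dataset ranged from 0.030 to 0.236.

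**Type I error**, equal missingness, 10 / 20 / 30% (Monte Carlo SE √(0.05 × 0.95 / 2000) = 0.005):
- without arm: 0.049 / 0.050 / 0.043;
- arm added but still one draw: 0.049 / 0.053 / 0.061.

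So adding arm alone is not the full remedy. It leaves the seed dependence, and at 30% missing the rejection rate is about two SEs above 0.05.

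**The case against.** The case for leaving this alone has substance.

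- **Six-month MLWHF is in the model.** It is measured after randomization and carries part of the treatment effect. A reader might infer that imputed values in both arms collapse to the same level, or that the effect is always diluted. The listed predictors do not support that: with 6-month values observed the loss is 3-8%, and a waning effect can turn it into a small gain. This stands.
- **The bootstrap is not shown to be wrong.** A reader might infer that the interval treats imputed values as observed. The SAP does not say whether imputation is repeated in each resample. This stands; the point is unspecified.
- **Missing MLWHF is not documented.** SAP 7 reports tests reduced or delayed by the pandemic, but its examples are hall walks and blood draws. Protocol 3.4.11.5 lets staff read the questionnaire to a subject who cannot complete it alone. Missing 12-month MLWHF is plausible, but no rate is given. This stands.
- **No decision hangs on 0.05.** The endpoint is nominal and has no success criterion. SAP 5.5 gives a win ratio without QoL, and SAP 3.2.4 and 6.2 analyse MLWHF directly. This lowers the stakes. It does not make an irreproducible p-value acceptable in an analysis meant to support labeling.
- **The draw might be deterministic.** If the predicted mean were used, the seed would not matter. The SAP does not say so, and the imputed values would still carry no allowance for their uncertainty.

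**Conclusion.** The concern holds in a limited form. The stated method tends to weaken the QoL tier, chiefly where 6-month MLWHF is missing as well, and a random draw leaves the nominal p-value and interval dependent on an unstated seed. Under an assumed 10-30% missing, a sustained 19.5-point effect and correlation 0.6, the loss in log win ratio is about 3-8% with 6-month values observed and 7-22% with them missing. It can reverse slightly if the effect wanes. The between-seed SD of z is about 0.12-0.26.

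A reader might take this as a risk of a false positive claim. The calculations do not support that for the method as written: type I error was 0.043-0.050 with equal missingness. It was not examined with unequal missingness. The usual cost is lost power and poor reproducibility in one nominal endpoint. The primary endpoint does not use this imputation.

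**What to change.** In SAP 3.2.2:

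1. Add randomized arm to the FCS model, or impute separately by arm.
2. Replace the single draw with multiple imputation, for example 50 sets. Compute the log win ratio and its SE in each set and combine them by Rubin's rules: total variance = W + (1 + 1/50)B, where W is the mean within-set variance and B the between-set variance. Take the p-value and interval from the pooled result. Alternatively, re-impute within each bootstrap resample and say so.
3. State the seed.
4. Delete the sentence that calls single imputation sufficient.

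Items 1 and 2 belong together: arm removes nearly all the shrinkage, and multiple imputation deals with the seed and the imputation uncertainty.

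The cost is a few lines of SAP text and a little more programming and computing. No new data are needed.
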